The condition is complex and is often described as a result of biological, psychological and social factors (1). Lifestyle factors such as smoking, obesity and low physical activity levels, which may lead to poorer overall health, are seen to be related to low back pain (1). Mental illness and psychological factors such as confidence in one's own ability and fear of movement are other factors that are related and may increase the risk of long-term problems (1,4,5).

Acute low back pain usually decreases over time, and the person can gradually return to previous activity level. However, recurrent episodes are common, about 30% experience having a new episode of low back pain within a year (1). For a small group, there is a risk of developing long-term problems (4). Long-term low back pain is seen as a condition where different patterns of pain may change over time (1,6).

According to World Health Organization (WHO), *physical activity* is defined as any body movement generated by skeletal muscles and requiring an increase in energy expenditure (7). *Physical exercise* is defined as a planned, structured and recurring physical activity aimed at maintaining or improving physical capacity such as fitness, mobility and strength (8). *Physical inactivity, or insufficient physical activity*, is defined as not meeting these recommendations (7). Studies have shown that patients with long-term low back pain have a low level of physical activity (9). There is no general definition of *Health-related quality of life* but refers to quality of life related to function and well-being in bad health, disease and treatment (10).

International guidelines focus on a biopsychosocial model when assessing and treating low back pain (11). This model includes information and advice on being physically active and, if possible, avoiding sick leave. It is also important to support self-care strategies. There is evidence for exercise training for patients with low back pain and physiotherapy is recommended as the first treatment option (11). However, there is still a lack of evidence which type of training has best effect (12,13). Both supervised and non-supervised training has been suggested to have effect on these patients well as daily physical activity such as Nordic walking (Hartvigsen et al-10, Matará-Peña-rocha et al-20, Quentin et al 21) (1,14,15). To reduce pain and increase functional capacity, patients with long-term low back pain are recommended daily physical activity. In addition, muscle strengthening exercise

and/or specific exercise for core stability¹ with or without the addition of aerobic exercise² is generally recommended (16). To achieve good adherence to exercise and training, patients with long-term low back pain demand better support from the healthcare, improved opportunities for supervised training and the use of new technology to visualize feedback (17).

The healthcare is facing major challenges and needs to be transformed. Health care closer to residents and more e-services are part of this transition. There is currently little knowledge about the effects of supervised digital physiotherapy training. Previous studies have shown that digital exercise training is as effective as traditional exercise for patients with long-term low back pain (18,19). Studies have also shown that digital training can contribute to increased accessibility and cost-effectiveness (20,21). However, there is a need to structurally evaluate supervised digital physiotherapy training in real time for patients with long-term low back pain.

During the pandemic, most training sessions were cancelled or performed at home, either on their own or via link. In Sweden, a daily home-training program on TV have had great impact during the pandemic, but also a large number of gym companies have offered supervised training via link both in real time and recorded during the last years. Digital training is an effective way to reach people and keep them interested to keep up with their training. It is therefore of interest to evaluate the effect of supervised training via link in this patient group.

Lack of reliable methods to determine what causes the pain (nonspecific back pain) makes it difficult to set a specific diagnosis. It is therefore of great importance that new methods are developed to improve the ability to the give a correct diagnose. Furthermore, the effect of different treatment on structural changes of the spine, e.g., different types of exercise, may guide how to best advice patients with different pathologies. With magnetic resonance imaging (MRI) an image of the spine can be obtained, but there is still a lack of evidence of its diagnostic benefit and knowledge if it can determine the origin of back pain. In a previous study using advanced MRI technology groups of individuals exposed to different exercise over a 3-month period demonstrated different disc patterns (22). Furthermore, new MRI techniques have demonstrated altered biodynamic properties on group level, when comparing patients with low back pain and control persons (23).

Purpose

The overall aim is to evaluate two different types of digital training interventions (aerobic, core stability) supervised by physiotherapists compared to daily physical activity in terms of clinical and patient-reported outcome (PROM) in patients with low back pain, both for short- and long-term. Furthermore, to evaluate whether new diagnostic MRI methods can identify longitudinal spine tissue changes and to analyse if there is an exercise-related difference (differences between the training groups). In addition, the ability to participate in the different exercise programs and their effect on pain in relation to baseline MRI findings will be evaluated.

Question / Hypothesis

- Do the clinical (muscle strength, conditioning, mobility, function/physical capacity) and PROM differ between patients with low back pain randomized to 3 different exercise interventions (aerobic, core stability, daily physical activity) after 6 and 12 months?

¹ the capacity of the lumbar-pelvic-hip muscle complex to control lower trunk movement and maintain stability of the vertebral column after skeletal perturbation.

² any activities that raise heart rate and make breathing somewhat harder

- Does patients' physical capacity change over time, and is there a difference between groups?
Does the training effect persist 12 months after ending the training intervention (6 months)?
- Can new diagnostic MRI methods identify characteristic changes over time in back tissue (disc/vertebra/muscle) in patients with low back pain in the full cohort and/or after different types of exercise intervention (aerobic, core stability, daily physical activity) after 6 - 12 months?
- Are MRI-verified changes in the back detected at base line associated the ability to participate in the training interventions as well as associated with positive effect (pain relief, increased endurance and muscle strength, etc.) after participating in any of the training intervention?
- Is there a relationship between clinical changes (pain, activity level and quality of life/function) and longitudinal changes in MRI verified components of the spine tissues depending on what type of exercise intervention (aerobic, core stability, daily physical activity)?

Hypothesis 1: Supervised digital training (aerobic and/or core stability) led by physiotherapist gives better results regarding clinical and PROM compared to self-training (daily physical activity), and the effect persists after ending the intervention (6 months) in patients with low back pain.

Hypothesis 2: new MRI methods can identify exercise-related changes in the lumbar spine in patients with nonspecific low back pain after undergoing supervised physiotherapy digital training (aerobic and/or core stability).

Hypothesis 3: there is a relationship between identified changes in low back tissues and the effect of different types of exercise interventions in patients with low back pain.

Method & Materials

Patients seeking primary health care (primarily Vänersborg/Trollhättan/Uddevalla, Sweden) for lower back pain will be asked to participate. Inclusion criteria: low back pain > 3 months, 18-50 years, have access to computer/tablet/mobile

Exclusion criteria:

- Inadequate Swedish as the language is an obstacle to be able to fully understand written and oral information regarding the project and to follow training instructions
- Other ongoing treatment/exercise for their low back pain
- Age > 50 years
- Patients with radiating leg pain and other neurological symptoms
- Previous back/neck surgery
- Pregnancy
- Diagnosed systematic diseases engaging the spine as rheumatoid arthritis, ankylosing spondylitis
- Factors that prevent an MRI examination, such as claustrophobia, metal implants, etc.

Patients who meet the inclusion criteria and agree to participate in the study will undergo a thorough clinical low back examination according to standard routine, and assessment of function and physical capacity performed by an experienced physiotherapist.

Before start, the patient will undergo MRI examination (NÄL, Trollhättan, Sweden) and functional imaging methods without contrast agents (such as diffusion tensor imaging (DTI), DIXON³, magnetic resonance spectroscopy (MRS) and T2 mapping⁴) will be obtained.

Sample size calculation regarding the training intervention: based on a p-value 0.05, power 0.85, SD 0.1 and a minimal clinical change in Visual Analog Scale (VAS)/pain 0.11 (Hawker et al-11) gives 23 people/group.

Sample size calculation regarding MRI: is based on the possibility of detecting a 0.5% difference (power size 0.041) regarding the T2 value between the three occasions with significance level 0.05 and power 0.8. Considering possible dropouts, we expect 30 patients in each group, a total of 90 patients.

Intervention

Training intervention

After completing the clinical low back examination, the patient will initially be randomized to either group 1 & 3, then 2 & 3 (see below). As more units will be included over time (Vänersborg/Trollhättan/Uddevalla, Sweden), we expect several training groups on-going at the same time.

Group 1 Aerobic

Group 2 Core stability

Group 3 Daily Physical Activity

Group 1 & 2 will be training according to the following program for 3 months: 45 minutes 3 times/week, 2 times digitally supervised by experienced physiotherapist and one-time un-supervised training. Then 3 months of un-supervised training with regular follow-up meetings with responsible physiotherapist.

Each training session includes warm-up, specific exercises with the ability adjust according to pain and function, and progression, then final relaxation exercises. Estimated number of participants/group (1&2): 10-12, inclusion rate about 35 patients first year, 35 patients 2nd year and 20 patients 3rd year (only preliminary calculation as we depend on the inclusion rate of patients and number of involved health care centre).

Group 3 (~10 patients will run concurrently with group 1or 2) will receive training instruction regarding daily physical activity equivalent to >150 min/week according to WHO recommendations (7) (11) (12) for 6 months. The activity will be recorded in a health app on the patient's mobile.

All patients (groups 1-3) will be able to continuously book a video appointment with the physiotherapist responsible for the training during the whole intervention period.

Any problems that cannot be solved during video consultation or at a follow-up examination will be referred back to the attending physician.

MRI scan

All included patients will be examined with MRI including T1- and T2-weighted sequences and functional imaging methods (such as DTI, DIXON and T2 mapping).

Data collection

Training intervention

³ a chemical shift imaging method

⁴ a magnetic resonance imaging technique used to calculate the T2 times of a certain tissue and display them voxel-wise on a parametric map.

Clinical examination of the low back will be performed according to standard routine (baseline – 6 months – 12 months) by an experienced physiotherapist. The examination will also include muscle strength tests and assessment of physical capacity.

At the same occasion, the patient will undergo MRI examination according to the protocol above. Responsible for the development of specific imaging methods and training of staff at the Imaging and Function Department is an experienced MRI physicist.

All clinical data will be recorded in the patient's medical record. All MRI scans will be archived as a medical record according to the hospital's regulations.

The patients will answer several questionnaires at the base line, 3 – 6 – 12 months. The questionnaires are registered in a web-based Survey & Reporting program (<https://webropol.se/>). The patients will receive mail or SMS with information when and how to answer the questionnaires.

The questionnaires include demographic data (based on questions included in SweSpine (<https://www.swespine.se/>), physical activity (<https://www.socialstyrelsen.se/>), as well as established and validated questionnaires regarding low back pain such as VAS (24), Oswestry Low Back Pain Disability Questionnaire (25), TAMPA scale of kinesiophobia (26), Hospital Anxiety and Depression Scale (HAD) (27), Swedish Version of the General Self-Efficacy Scale (28) and EQ-5D-5L (29)

Analysis of MRI examination

Conventional radiological categorization schemes (identification of high intensity zones = HIZ in the intervertebral discs and Modic changes in the vertebrae), as well as advanced analysis methods (e.g. histogram analysis, shape/texture analysis and regional analysis) will be used for detailed characterization of the vertebrae/disc/muscle.

The MR images will be assessed according to clinical routine and in addition, when relevant, according to conventional classification systems for specific morphological changes such as Modic Types, Schmorls nodules, High-Intensity Zones. New objective tissue characteristic measures (histogram analysis, shape/texture analysis and regional analysis) in vertebrae/disc/muscle will be extracted by the software we previously have developed and validated based on artificial intelligence (histogram analysis, shape/texture analysis and regional analysis) (30)

Data analysis

All data will be documented in a separate database. This database will be password protected and only those directly involved in the study will have access to the database. In addition, all personal data will be pseudonymised according to EU general data protection rules (GDPR) before exported into SPSS (<https://www.ibm.com/products/spss-statistics>). Data will only be analysed at the group level.

The questionnaires in Webropol will be exported to SPSS for analysis.

Descriptive statistics will be presented as mean/standard deviation or median/range. Comparisons between and within groups will be conducted using either parametric or non-parametric statistical methods depending on data quality. Bonferroni correction will be performed when multiple comparisons are done. All statistical tests will be 2-tailed with statistical significance level of $p < 0.05$.

Spearman rank correlation will be used analysing the association between specific morphological changes and clinical data. In addition, multiparametric prediction modelling will be performed (based on unsupervised/supervised machine-learning).

Expected result / Clinical relevance

By offering patients supervised training led by experienced physiotherapist, we hope for high compliance and thus improved chance for a high-quality study evaluating the result of the different training programs. Muscle strength exercises and specific exercise programs to improve trunk control as well as aerobic physical exercise to reduce pain and increase physical capacity and functional capacity are already well-established treatment methods for patients with long-term low back pain (14-16) (30,31,32). However, research has shown that patients demand better support from healthcare where patients wanted to use technology to visualize feedback and improved opportunities to be guided in their training (17). A previous randomised trial compared supervised physiotherapist-led exercise and "unsupervised" home exercise and found supervised training more effective regarding several patient-related outcome measures, such as pain, health-related quality of life, and function (7) (14). With a personal and regular contact with the physiotherapist digitally, the present study setup provides such support which in turn likely improves patient related outcomes.

To evaluate whether the effect of daily physical activity is comparable to more exercise-intensive programs is important since if this can be shown the likelihood that more people continuing being physically active increases which in turn contributes to also other health-promoting effects. The detailed longitudinal MRI evaluation deepen the knowledge regarding how different physical activity affect the spinal tissues and has the potential to provide improved diagnostics for patients with low back pain.

Our previous study regarding monitoring the effect of exercise in healthy subjects was for the first time able to objectively measure the effects of different types of exercise on the disk.

References

2. GBD 2017 Disease and Injury Incidence and Prevalence Collaborators. Global, regional, and national incidence, prevalence, and years lived with disability for 328 diseases and injuries for 195 countries, 1990-2017: a systematic analysis for the Global Burden of Disease Study 2017 Lancet 2018;392:1789-858.

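### The pain sample size of 23 per group does not follow from the inputs printed beside it; an ordinary two-sided t-test on those inputs needs 16

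*Protocol*

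**What the plan says.** The sample size paragraph in Method & Materials gives four inputs for the training comparison, "based on a p-value 0.05, power 0.85, SD 0.1 and a minimal clinical change in Visual Analog Scale (VAS)/pain 0.11", and says that this "gives 23 people/group". It names no test and no adjusted alpha, and does not say whether the SD is that of the score or of the change. Dropout comes in afterwards, at the end of the following MRI paragraph: "Considering possible dropouts, we expect 30 patients in each group, a total of 90 patients". No dropout rate is given.

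The remaining elements are in other sections. Question / Hypothesis sets out a comparison of patients "randomized to 3 different exercise interventions (aerobic, core stability, daily physical activity) after 6 and 12 months". Data analysis fixes the sidedness ("All statistical tests will be 2-tailed with statistical significance level of" 0.05), leaves the type of test open ("Comparisons between and within groups will be conducted using either parametric or non-parametric statistical methods depending on data quality") and adds that "Bonferroni correction will be performed when multiple comparisons are done".

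**The concern.** The sentence presents 23 as the result of its inputs, and every input needed for a standard calculation is printed. The result is nevertheless 44% above what that calculation gives (23/16 = 1.44). This is more than rounding, or the gap between a normal approximation and an exact t calculation.

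It is the protocol's only power statement for pain, so two things are at stake. A reader cannot reproduce it. Nor can a reader tell whether 23 already allows for the Bonferroni correction across three groups, or whether that correction will be taken out of the power later.

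**Working it through.** **Inputs.** Alpha 0.05, power 0.85, SD 0.1 and difference 0.11 (sample size paragraph); two-sided tests (Data analysis); equal groups (30 planned in each of three). Standardised difference d = 0.11/0.1 = 1.10.

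**Attempt to reproduce 23.**

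1. Normal approximation: n = 2(z₀.₉₇₅ + z₀.₈₅)²/d² = 2(1.960 + 1.036)²/1.21 = 14.8, so 15 per group.
2. Exact two-sample t-test (noncentral t, 2n − 2 degrees of freedom, noncentrality d√(n/2)): n = 15.86, so 16 per group. Power is 0.828 at n = 15, 0.853 at n = 16 and 0.954 at n = 23.

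**Other readings of the printed inputs, two-sided unless noted, overall level 0.05, power 0.85.**

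| Reading | n per group |
|---|---|
| t-test, one-sided | 13 |
| Paired t-test, SD of change 0.1 | 10 |
| Paired t-test, effect 1.10/√2 | 17 |
| Rank-sum test, normal data (simulated: 0.827 at 16, 0.853 at 17) | 17 |
| Rank-sum test at the worst-case efficiency 0.864 (15.86/0.864 = 18.4) | 19 |
| Three-group ANOVA, means 0, 0, 0.11 (f = 0.519; 14.59) | 15 |
| Three-group ANOVA, means 0, 0.055, 0.11 (f = 0.449; 19.09) | 20 |
| Kruskal-Wallis, normal data, same two patterns of means (simulated) | 16 and 21 |
| Two Bonferroni t-tests, alpha 0.025 (19.08) | 20 |
| Three Bonferroni t-tests, alpha 0.0167 (20.94) | 21 |

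None gives 23.

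**Routes that do reach 23.** Each needs something that the sentence does not state.

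- Three pairwise rank-sum tests at 0.0167, normal data: simulated power 0.849 at n = 22 and 0.871 at n = 23.
- A three-group rank test, or two rank-sum tests at 0.025, sized at the 0.864 bound: 19.09/0.864 = 22.10 and 19.08/0.864 = 22.08.
- Four Bonferroni t-tests (alpha 0.0125): 22.26.
- Power 0.95 instead of 0.85: 22.49.
- SD 0.12 with difference 0.11, unadjusted t-test: 22.4.
- Difference and SD exchanged (0.10 and 0.11), unadjusted t-test: 22.73.
- Dropout of 30% added to 16: 16/0.70 = 22.9. No such rate is stated, and dropout is already the reason given for 30 per group.

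**Power of 23 evaluable per group on the printed inputs.**

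| Test | 1 comparison | 2 (Bonferroni) | 3 (Bonferroni) |
|---|---|---|---|
| t-test | 0.95 | 0.92 | 0.89 |
| Rank-sum, normal data | 0.94 | 0.90 | 0.87 |
| Rank-sum at efficiency 0.864 | 0.92 | 0.87 | 0.83 |

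**Why the cause matters.** If the difference and SD were exchanged, 23 per group has t-test power 0.854 for one comparison but 0.722 for three Bonferroni comparisons, and 30 evaluable per group would be needed for 0.851. With an SD of 0.12 the corresponding figures are 0.860, 0.730 and 0.857. Neither cause is shown by the protocol; the figures only show how far the answer depends on it.

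**The case against.** The strongest reply is that the protocol never says the calculation was an unadjusted two-group t-test. Data analysis allows non-parametric methods and calls for Bonferroni correction, and there are three groups. Three pairwise rank-sum tests at 0.0167 use the printed difference, SD and power, and the smallest n reaching 0.85 in simulation is 23. The SD is printed to one decimal, so 0.12 could have been rounded to 0.1, and the plain t-test then gives 23 as well. On this view no calculation has been shown to be wrong. The test details may sit in a statistical analysis plan that is not at hand, and 23 is conservative in any case.

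Much of this stands. An unstated step is as possible as a misprint. The figure 16 belongs to one unadjusted comparison and is not a recommended size for this trial: at 16 per group, three Bonferroni t-tests would have power of only 0.715. It is also true that on the printed inputs 23 is ample.

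The reply does not rescue the sentence. It claims a result from four printed inputs, and each route to 23 changes or adds to them. The routes disagree about the test, the alpha and the SD, and imply different power for the comparisons the trial will make. A later analysis plan may choose the test, but it cannot make the printed derivation follow from the printed inputs.

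**Conclusion.** The concern holds, as a minor point. On the printed inputs a two-sided two-sample t-test needs 16 per group against the stated 23, and 23 per group gives power 0.95 against the stated 0.85. The other standard readings at an overall 0.05 fall between 10 and 21. This rests on taking the printed values as exact and the groups as equal in size. The simulated rank-test figures also assume normal data.

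The protocol does not show whether a step was left out or a value misprinted. On the printed inputs the discrepancy is on the safe side: 23 evaluable per group keep 0.89 power for three Bonferroni t-tests, and 30 per group are to be enrolled. That reassurance lasts only if the printed difference and SD are confirmed.

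**What to change.** Retrieve the original calculation and correct the sentence so that the test, the per-comparison alpha, the difference, the SD (of score or of change), the VAS scale, the power and n agree. Say whether n includes the Bonferroni correction and for how many comparisons.

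If the printed inputs and an unadjusted t-test are confirmed, the text could read:

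> With a two-sided two-sample t-test at 0.05, SD 0.1 and a VAS difference of 0.11, 16 evaluable patients per group give power 0.85; the planned 23 evaluable per group give 0.95 (0.89 if three pairwise comparisons are Bonferroni-adjusted).

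If another test, alpha or SD was used, print it and recompute the power of 23 per group for that case. Inputs should not be chosen afterwards to fit 23, and the sample should not be cut to 16.

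The cost is one sentence after a check of the file, with no extra patients and no design change. The downside is that the stated power may become less favourable if an input proves to be misprinted.

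### The Protocol describes randomisation only within two pairs (1 v 3, then 2 v 3) but asks a question about three randomised groups; on that reading aerobic v core stability is not a randomised comparison

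*Protocol*

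**What the plan says.** Under Intervention, Training intervention, the Protocol states that after the clinical examination "the patient will initially be randomized to either group 1 & 3, then 2 & 3". Group 1 is aerobic training, Group 2 core stability and Group 3 daily physical activity. The next sentence adds that, as units join, "we expect several training groups on-going at the same time". Further down, "Group 3 (~10 patients will run concurrently with group 1or 2"), and classes in Groups 1 and 2 are put at 10 to 12 people. No other section describes allocation, and no allocation ratio is given.

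The Question / Hypothesis section asks whether outcomes differ between patients "randomized to 3 different exercise interventions (aerobic, core stability, daily physical activity"). The Purpose section sets an MRI aim "to analyse if there is an exercise-related difference (differences between the training groups"). Hypothesis 1 is that supervised training "gives better results regarding clinical and PROM compared to self-training (daily physical activity").

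The sample size text in Method & Materials says "we expect 30 patients in each group, a total of 90 patients", and the Training intervention section gives an "inclusion rate about 35 patients first year, 35 patients 2nd year and 20 patients 3rd year". The Data analysis section plans comparisons between and within groups, with Bonferroni correction for multiple comparisons, and does not mention pair, wave or unit.

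**The concern.** The allocation sentence names two separate randomisations and does not say that the choice of pair is itself random. If so, whether a patient enters the aerobic pair or the core stability pair depends on when and where that patient was recruited. Two kinds of comparison then lose the protection of randomisation:

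- aerobic v core stability directly;
- either training group v all of Group 3, because the controls from one pair were never randomised against the other training group.

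An analysis that takes the Question / Hypothesis section at its word would treat all of these as randomised. Differences in calendar time, unit or case mix could then be read as effects of the training programme. If the pair of each Group 3 patient is not recorded, the analysis cannot undo this. Analysing within pairs is valid but leaves fewer controls per contrast than the planned 23.

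**Working it through.** **1. The texts side by side.** The Training intervention section has two randomisations, 1 v 3 and 2 v 3. The Question / Hypothesis section has patients randomised to three interventions and a question about differences between them. Under the first description:

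| Comparison | Randomised? |
|---|---|
| 1 v the Group 3 patients of its pair | yes |
| 2 v the Group 3 patients of its pair | yes |
| 1 v 2, direct | no |
| 1 or 2 v all of Group 3 | only in part |
| (1 − own Group 3) − (2 − own Group 3) | rests on the randomisation, if training effects do not depend on the pair |

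**2. Do the planned sizes settle the reading?** The total reproduces: 3 × 30 = 90 and 35 + 35 + 20 = 90. Let *a* be the class size, 10 to 12.

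- If every class has its own 10 or so controls, Group 3 = 90 × 10/(*a* + 10) = 45.0, 42.9 or 40.9 for *a* = 10, 11, 12. That is not 30.
- If one set of 10 controls serves one class of each training group, a set has 2*a* + 10 = 30, 32 or 34 patients. That is close to 35 a year, and three sets with *a* = 10 give 30/30/30.
- 2:1 allocation within each pair (30 v 15) also gives 30/30/30.

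So the sizes are reachable, but only with a ratio or a sharing of controls that the Protocol does not state.

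**3. Precision and power.** Inputs from the sample size text and Data analysis: difference 0.11, SD 0.1 (so 1.1 SD), two-sided alpha 0.05, Bonferroni for multiple comparisons. The number of comparisons is not given, so I show one, two and three (0.05, 0.025, 0.0167).

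Assumptions: two pairs of 45 patients, and the loss implied by 30 recruited and 23 required. That leaves 45 × 23/30 = 34.5 patients per pair, split either 2:1 (23 v 11 or 12) or about 1:1 (18 v 17).

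Training group v own controls: SE = √(1/n + 1/c) in SD units, df = n + c − 2, power from the noncentral t distribution.

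| n v c | SE | 0.05 | 0.025 | 0.0167 |
|---|---|---|---|---|
| 23 v 11 | 0.367 | 0.829 | 0.739 | 0.681 |
| 23 v 12 | 0.356 | 0.850 | 0.767 | 0.712 |
| 18 v 17 | 0.338 | 0.884 | 0.812 | 0.763 |
| 23 v 23, three-way randomised | 0.295 | 0.954 | 0.916 | 0.888 |

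Indirect 1 v 2 through each pair's own controls: SE = √(2(1/n + 1/c)), df = 2(n + c) − 4.

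| n, c per pair | SE | 0.05 | 0.025 | 0.0167 |
|---|---|---|---|---|
| 23, 11.5 | 0.511 | 0.564 | 0.449 | 0.387 |
| 18, 17 | 0.478 | 0.620 | 0.506 | 0.443 |

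A direct randomised 23 v 23 has SE √(2/23) = 0.295. A linear model with pair and group gives the same SE for 1 v 2 as the indirect formula (0.504 with c = 12, 0.518 with c = 11). Adding pair as a factor therefore turns the 1 v 2 estimate into the indirect one.

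**The case against.** The strongest reply is that there is no contradiction: a trial that randomises 1 v 3 and 2 v 3 does, taken as a whole, have patients randomised to three interventions. The word *initially* may also cover only a start-up phase, with three-way allocation once several classes run at once. Both readings are possible, but neither removes the problem. On the first, the three-group question still includes a contrast that was not randomised. On the second, the Protocol never says when or how three-way allocation begins, and the start-up patients remain randomised only within a pair.

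Several other points stand and limit the scope:

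- The overall aim and Hypothesis 1 compare supervised training with daily activity, and the within-pair contrasts answer them. Pooling the two training groups, stratified by pair, loses no precision: with 2:1 pairs the SE is √(0.5 × (1/23 + 1/11.5)) = 0.255 SD, the same as √(1/46 + 1/23) = 0.255 SD for 46 v 23 under three-way randomisation.
- At alpha 0.05 the own-pair power is about the planned 0.85. The shortfall appears only under Bonferroni, for an assumed number of contrasts.
- The figure of 0.95 for 23 v 23 is itself above the planned 0.85, so part of the apparent loss is surplus.
- The 1.1 SD is the plan's general VAS input, not a stated difference between two training programmes, so the 1 v 2 powers are illustrative.
- The size of any bias by wave or unit cannot be derived from the document.
- The class sizes and accrual are labelled as estimates, and they can be made to fit 30/30/30.

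It is also true that the Data analysis section does not prescribe a naive pooled analysis. An analysis plan may add pair or wave, but it cannot make aerobic v core stability a randomised comparison.

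**Conclusion.** The concern holds and should be fixed. As written, the allocation scheme and the three-group question do not agree. On the plain reading, neither aerobic v core stability nor each training group v all of Group 3 is a fully randomised comparison. Each training group v its own-pair controls is randomised, so Hypothesis 1 survives.

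Under the pair sizes assumed above, own-pair power is 0.83–0.88 at alpha 0.05, 0.74–0.81 with two Bonferroni contrasts and 0.68–0.76 with three. The indirect aerobic v core stability estimate has a standard error 0.478/0.295 = 1.6 to 0.511/0.295 = 1.7 times that of a direct randomised 23 v 23. That the text describes no randomisation between Groups 1 and 2 is certain. Whether the sponsor intended this cannot be told from the document.

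**What to change.** Reconcile the Question / Hypothesis and Training intervention sections in one of two ways.

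**Keep the pairs (the cheaper option).** Record for every Group 3 patient the training group against which that patient was randomised. Compare each training group with the Group 3 patients of its own pair, or include pair or wave and unit as factors. Replace the wording in Question / Hypothesis with, for example:

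> Aerobic v daily physical activity and core stability v daily physical activity are randomised comparisons, each within its own pair. A direct comparison of aerobic with core stability is non-randomised and exploratory. An indirect comparison, the difference between the two within-pair effects, rests on the randomisation but is much less precise.

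The cost is wording and one recorded variable, with fewer controls per contrast and a weaker aerobic v core stability claim.

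**Randomise three ways.** For patients not yet allocated, randomise among all three groups within unit and wave, and correct the Training intervention section. The cost is an amended randomisation list and possibly a longer wait to fill classes. Patients already allocated stay in within-pair comparisons.

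In both cases it would help to state what *initially* covers, the allocation ratio, and whether one set of Group 3 patients serves both an aerobic and a core stability class.
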